# 3. Genetic Testing N/A 🖂

## A. Describe

- i. the types of future research to be conducted using the materials, specifying if immortalization of cell lines, whole exome or genome sequencing, genome wide association studies, or animal studies are planned
- ii. the plan for the collection of material or the conditions under which material will be received
- iii. the types of information about the donor/individual contributors that will be entered into a database
- iv. the methods to uphold confidentiality
- B. What are the conditions or procedures for sharing of materials and/or distributing for future research projects?
- C. Is widespread sharing of materials planned?
- D. When and under what conditions will materials be stripped of all identifiers?
- E. Can donor-subjects withdraw their materials at any time, and/or withdraw the identifiers that connect them to their materials?

- i. How will requests to withdraw materials be handled (e.g., material no longer identified: that is, anonymized) or material destroyed)?
- F. Describe the provisions for protection of participant privacy
- G. Describe the methods for the security of storage and sharing of materials
- 4. **Subject Population:** Provide a detailed description of the types of human subjects who will be recruited into this study.

A total of 10 participants, 18 years of age or older will be enrolled. Participants must have a diagnosis of AA, AT or AU.

5. Subject classification: Check off all classifications of subjects that will be specifically recruited for enrollment in the research project. Will subjects who may require additional safeguards or other considerations be enrolled in the study? If so, identify the population of subjects requiring special safeguards and provide a justification for their involvement.

Children	Healthy	Fetal material, placenta, or dead fetus
Non-English Speaking	Prisoners	Economically disadvantaged persons
Decisionally Impaired	Employees	Pregnant women and/or fetuses
Vale Students	Females of ch	ildbearing potential

NOTE: Is this research proposal designed to enroll children who are wards of the state as potential subjects? 
Yes No (If yes, see Instructions section VII #4 for further requirements)

6. **Inclusion/Exclusion Criteria:** What are the criteria used to determine subject inclusion or exclusion?

Patients will be included in the study if all of the following conditions are met:

- Age  $\geq$  18-years old
- Diagnosis of AA with at least 2 patches of alopecia involving the scalp, AT or AU
- Stable hair loss present for 6 months or longer
- No treatment for alopecia areata in the past 1 month
- No evidence of spontaneous hair regrowth

Patients will be excluded from the study if any of the following conditions are met:

- Age <18 years old
- Patients have received treatment known to affect alopecia areata within 1 month of enrolling in the study
- Patients whose current episode of AT or AU is more than 5 years
- Patients with a history of malignancy (except history of successfully treated basal cell or squamous cell carcinoma of the skin)
- Patients known to be HIV or hepatitis B or C positive

## Page 10 of 26

- Patients with positive tuberculin skin test or positive QuantiFERON® TB test
- Patients with leukopenia or anemia
- Patients with renal or hepatic impairment
- Patients taking immunosuppressive medications, including but not limited to prednisone, methotrexate, mycophenolate mofetil, azathioprine, tacrolimus, cyclosporine, or TNF-α inhibitors
- Women who are pregnant or nursing
- 7. How will **eligibility** be determined, and by whom?

Eligibility will be determined by the PI, [name], PhD and/or co-investigator [name]. Patients will be evaluated in person at a regular clinic appointment to determine if they meet inclusion criteria.

8. **Risks:** Describe the reasonably foreseeable risks, including risks to subject privacy, discomforts, or inconveniences associated with subjects participating in the research.

The risks associated with oral tofacitinib are listed below:

- Infections, including severe and opportunistic infections
- Viral reactivation
- Neutropenia
- Lymphopenia
- Anemia
- Malignancy
- Lymphoma
- Gastrointestinal perforation
- Headache
- Diarrhea
- Increased liver transaminases
- Increased creatinine
- Increased cholesterol

The above risks are very unlikely likely to occur with topical administration given what is known about transepidermal absorption and minimal surface area of application in this trial. Therefore, the only reasonably foreseeable risk is irritation at the site of application. There are no other known risks to the study.

9. **Minimizing Risks:** Describe the manner in which the above-mentioned risks will be minimized.

Screening visit will allow for exclusion of patients who do not meet inclusion criteria. Maximum time on treatment will be 6 months. Patients will undergo clinical evaluation every month during treatment and labs will be monitored at 1 and 6 months of treatment. Surface area of application will be limited to the scalp.

- 10. **Data and Safety Monitoring Plan:** Include an appropriate Data and Safety Monitoring Plan (DSMP) based on the investigator's risk assessment stated below. (Note: the HIC will make the final determination of the risk to subjects.) For more information, see the Instructions, page 24.
  - a. What is the investigator's assessment of the overall risk level for subjects participating in this study? Minimal risk
  - b. If children are involved, what is the investigator's assessment of the overall risk level for the children participating in this study? N/A
  - c. Copy, paste, and then tailor an appropriate Data and Safety Monitoring Plan from http://www.yale.edu/hrpp/forms-templates/biomedical.html for
    - i. Minimal risk
    - ii. Greater than minimal/moderate risk
    - iii. High risk

## Minimal Risk DSMP

The principal investigator is responsible for monitoring the data, assuring protocol compliance, and conducting the safety reviews monthly. During the review process the principal investigator will evaluate whether the study should continue unchanged, require modification/amendment, or close to enrollment.

The principal investigator (monitor) or the Institutional Review Board (IRB) have the authority to stop or suspend the study or require modifications.

This protocol presents minimal risks to the subjects and Unanticipated Problems Involving Risks to Subjects or Others (UPIRSOs), including adverse events, are not anticipated. In the unlikely event that such events occur, Reportable Events (which are events that are serious or life-threatening and unanticipated (or anticipated but occurring with a greater frequency than expected) and possibly, probably, or definitely related) or Unanticipated Problems Involving Risks to Subjects or Others that may require a temporary or permanent interruption of study activities will be reported immediately (if possible), followed by a written report within 5 calendar days of the Principal Investigator becoming aware of the event to the IRB (using the appropriate forms from the website) and any appropriate funding and regulatory agencies. The investigator will apprise fellow investigators and study personnel of all UPIRSOs and adverse events that occur during the conduct of this research project as they are reviewed by the principal investigator. The protocol's research monitor, co-investigators and Pfizer will be informed of adverse events within 5 days of the event becoming known to the principal investigator.

11. Statistical Considerations: Describe the statistical analyses that support the study design.

This will be a pilot study that will be primarily observational in nature, and statistics will be purely descriptive. Pre-and post-treatment SALT scores will be compared for individual patients, and the mean change in score values from baseline will be described. Clinical photographs will be used to demonstrate presence or absence of hair regrowth.

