tofacitinib will be applied to up to half of the alopecic patches (no more than 4 patches). In participants with AT or AU, tofacitinib 2% ointment will be applied to half of the scalp. Topical tofacitinib will be applied twice daily. Patients will wash their hands prior to and following application of the ointment. Patients demonstrating hair regrowth in the tofacitinib application sites will subsequently apply tofacitinib ointment to all involved sites when evidence of regrowth is observed at the initial sites of application. Treatment will be discontinued when either full regrowth has occurred in areas of application or at 6 months of treatment, whichever comes first. If a clinically significant adverse effect (lab abnormality or patient-reported adverse effect) is encountered, then the application frequency will be decreased to once daily. In the case of a serious adverse effect, tofacitinib ointment will be immediately discontinued.

Screening labs will include *QuantiFERON®* TB gold or PPD, fasting lipid panel, complete metabolic panel, and complete blood count with differential. Females of childbearing potential will require a negative pregnancy test prior to initiating treatment. While on treatment, participants will be evaluated every 4 weeks. Physical exam of the skin with special attention to presence or absence of hair growth, photographs of the skin, as well as a complete review of systems (headache, dizziness, fever, cough, shortness of breath, nausea, vomiting, diarrhea) will be performed at each visit. Severity of Alopecia Tool (SALT) will be used to score alopecia severity prior to and at the end of treatment, and the change in SALT score will be measured. Visits will take place at Yale Dermatology – Middlebury or Yale Dermatology Associates. Patients will be evaluated monthly for a maximum of 6 months. As above, patients who experience complete hair growth prior to 6 months will discontinue therapy at the visit when full hair growth has occurred. Labs will be monitored at 1 month and at completion of therapy, which for most patients will be after 6 months of treatment, and will include fasting lipid panel, complete blood count with differential, and complete metabolic panel. This will require 2-3 vials or approximately 6-12 mL of blood at each blood draw).

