## SECTION VIII: PROTECTION OF RESEARCH SUBJECTS

#### Confidentiality & Security of Data:

a. What protected health information (medical information along with the HIPAA identifiers) about subjects will be collected and used for the research?

Name, age, gender, race, age of onset of alopecia areata and subsequent natural history (including episodes of regrowth and recurrence), prior therapies, comorbid conditions, percent scalp involvement of hair loss at initial presentation and follow-up visits (as measured via Severity of Alopecia Tool – SALT score), involvement of eyebrows, eyelashes and body hair, treatment including dose and duration, response to treatment, adverse effects

b. How will the research data be collected, recorded and stored? Laptop 1 with patient data in an Excel spreadsheet with a code identifier for each patient. The code identifiers will be stored separately on a different laptop computer. The laptops are encrypted with Yale security software.

- c. How will the digital data be stored? CD DVD Flash Drive Portable Hard Drive Secured Server Laptop Computer Desktop Computer Other
- d. What methods and procedures will be used to safeguard the confidentiality and security of the identifiable study data and the storage media indicated above during and after the subject's participation in the study?
  Study participants will be identified with a code number. Codes will be maintained in a separate file. All data will be kept in password-protected files on an encrypted Yale laptop. Do all portable devices contain encryption software? Xes No
  If no, see http://hipaa.yale.edu/guidance/policy.html
- e. What will be done with the data when the research is completed? Are there plans to destroy the identifiable data? If yes, describe how, by whom and when identifiers will be destroyed. If no, describe how the data and/or identifiers will be secured.

Code identifiers will be destroyed by [name] by deleting the file so that the data is deidentified. The de-identified data will be kept for two years.

f. Who will have access to the protected health information (such as the research sponsor, the investigator, the research staff, all research monitors, FDA, Yale Cancer Center Data and Safety Monitoring Committee (DSMC), SSC, etc.)? (please distinguish between PHI and de-identified data)

[name], [name], [name], YSM3, Yale Human Investigation Committee, Pfizer, Food and Drug Administration

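### The only numerical efficacy summary is change in a whole-scalp SALT score, which pools initially treated and untreated areas; no by-site scoring or summary is planned

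*Combined protocol and SAP*

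**What the plan says.** Section V, item 3 (Research Plan) sets unequal exposure within each patient. In alopecia totalis (AT) or universalis (AU), "tofacitinib 2% ointment will be applied to half of the scalp". In alopecia areata (AA), "tofacitinib will be applied to up to half of the alopecic patches (no more than 4 patches". All involved sites are treated only "when evidence of regrowth is observed at the initial sites of application". AA patients must have at least two scalp patches (item 6), so every patient begins with an involved area that receives no drug. It stays untreated until extension, or throughout if regrowth is never seen.

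Each 4-weekly visit includes "Physical exam of the skin with special attention to presence or absence of hair growth, photographs of the skin". SALT "will be used to score alopecia severity prior to and at the end of treatment". On stopping, "patients who experience complete hair growth prior to 6 months will discontinue therapy".

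Item 11 (Statistical Considerations) describes the study as a descriptive pilot. Its efficacy plan is "Pre-and post-treatment SALT scores will be compared for individual patients, and the mean change in score values from baseline will be described", plus photographs showing whether hair regrew. Section VIII, item a, describes SALT as "percent scalp involvement of hair loss at initial presentation and follow-up visits", which makes it a score for the scalp as a whole. No section plans a score, count or contrast by treated and untreated site.

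**The concern.** The study is open label and Section VI marks placebo as not applicable, so the initially untreated area is the only concurrent comparison. The planned analysis does not use it. A percent-of-scalp score adds regrowth where drug was applied to regrowth where it was not, or was applied only later.

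The entry criteria (hair loss stable for 6 months or longer, no evidence of spontaneous regrowth) make spontaneous regrowth less likely during the study but cannot exclude it. Section IX hopes the results may serve as proof of concept. For that, the useful observation is whether hair returned first, or more, where the ointment went. The planned mean SALT change cannot show this.

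**Working it through.** The plan states no power, effect size or variability, so there is no figure to reproduce. The check is whether different local results can give the same planned summary.

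**Inputs from the documents.** Half of the scalp is treated at the start in AT/AU. Extension follows observed regrowth at the initial sites. Treatment lasts at most 6 months. The Background describes AT as complete loss of scalp hair, so baseline SALT is taken as 100; AU is taken likewise.

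**Assumptions, not in the documents.** Regrowth, once begun, runs at 15 percentage points a month. It counts as seen at the first monthly visit with at least 5 points in the treated half, and extension happens then. Visits are treated as monthly.

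**Formula.** With T and U the percent regrowth in the initially treated and initially untreated halves:

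SALT fall = 0.5 × T + 0.5 × U; by-site difference = T − U.

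**Path A: local drug effect, 2.5-month lag in each area.** At month 3, T = 15 × (3 − 2.5) = 7.5, so extension occurs then. At month 6, T = 15 × (6 − 2.5) = 52.5. The second half, treated from month 3, begins to regrow at month 5.5, so U = 15 × (6 − 5.5) = 7.5.

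**Path B: no drug effect, spontaneous regrowth in both halves from month 4.** At month 5, T = U = 15, so extension is triggered but changes nothing. At month 6, T = U = 15 × (6 − 4) = 30.

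| Month | A: T / U | A: T − U | B: T / U | B: T − U |
|---|---|---|---|---|
| 1 | 0 / 0 | 0 | 0 / 0 | 0 |
| 2 | 0 / 0 | 0 | 0 / 0 | 0 |
| 3 | 7.5 / 0 | 7.5 | 0 / 0 | 0 |
| 4 | 22.5 / 0 | 22.5 | 0 / 0 | 0 |
| 5 | 37.5 / 0 | 37.5 | 15 / 15 | 0 |
| 6 | 52.5 / 7.5 | 45 | 30 / 30 | 0 |

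SALT fall at month 6: A, 0.5 × 52.5 + 0.5 × 7.5 = 30; B, 0.5 × 30 + 0.5 × 30 = 30. The planned summary is identical; the by-site differences are 45 and 0.

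**AA.** The weight on the treated area is not fixed. With patches of equal size (assumed) and the largest number allowed treated, it is 1/2 for two patches, 1/3 for three, 4/10 for ten and 4/12 for twelve. The same local result therefore moves SALT by different amounts in different patients.

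**Which visit to summarise.** A no-effect simulation assumed onset independently in each area with a 20% or 40% chance, uniform over 6 months, then 10 or 20 points a month, with extension at the first visit with at least 5 points. Taking each patient's difference at the visit that triggers extension, or at month 6 if there is none, gives a mean of about −4 to −13 points although nothing is happening. Patients without extension are selected for having little regrowth in the treated area, and they outweigh the rest. If all patients share one onset time across both areas, the bias is 0; if half do, it is −1.8 to −6.4. At any fixed visit the mean is 0 within simulation error, provided the two areas are exchangeable, which the documents do not secure.

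**The case against.** The strongest reply is that the plan already yields by-site information. The scalp is examined and photographed at every visit, individual patients are compared, and the extension rule obliges someone to judge regrowth at the initial sites. In 10 patients described without tests, a reader could look at the photographs. This is right as to raw material, and one should not infer that by-site information is never collected. But it is qualitative, no by-site record or summary is planned, and the only numbers reported pool the areas.

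A second reply is that a by-site contrast would still be weak evidence, since neither random choice of sites nor blinded scoring is described. That stands: the contrast would be supportive, not decisive.

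Two stronger readings are tempting and should not be drawn:

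- One could show the ambiguity without extension, for example treated/untreated regrowth of 60/0, 45/15 or 30/30, each a 30-point fall. Regrowth at the initial sites triggers extension, so such patients would not normally remain unextended. The illustration above therefore follows the rule.
- One could read the SALT timing as a contradiction: before and at the end of treatment in Section V, follow-up visits in Section VIII. The latter is a list of health information, not a schedule, and an end-of-treatment visit is also a follow-up visit. The wording is loose, no more.

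**Conclusion.** The concern holds as a gap in the analysis plan. Every patient starts with an untreated involved area, and the sole numerical efficacy summary cannot use it. That SALT change pools the areas follows from the documents and needs no assumption. The size, a by-site difference of 45 or 0 behind the same 30-point fall, depends on the assumed lag, rate and visibility threshold and is illustrative only.

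A reader might go further and infer that the planned analysis is wrong or the study uninformative. The documents do not support that: they promise description only, and whole-scalp change remains a legitimate description. This is an inexpensive improvement in interpretability that should be made, not a correction of a stated figure.

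**What to change.** In Section V, item 3: at baseline and at each existing 4-weekly visit, score percent hair loss separately in the initially treated and initially untreated scalp areas, before any extension at that visit.

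In item 11, keep the whole-scalp SALT change and add a descriptive listing of each patient's by-site values and treated-minus-untreated difference at every visit, with the extension visit marked and the number still observed. Give any mean by-site difference at fixed visits, not at a visit chosen by response. Do not make the first 4-week visit the main summary: it may precede visible regrowth, and in the illustration it is 0 under both paths.

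State the limits: differences after extension are diluted, patients with complete regrowth stop early, and neither random site choice nor blinded scoring is described. Align the SALT timing wording in Sections V and VIII at the same time.

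The cost is brief extra scoring at visits where the scalp is already examined and photographed, a few data columns, and two short text changes. No patients or visits are added, and no treatment rule changes.

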# SECTION VI: RESEARCH INVOLVING DRUGS, BIOLOGICS, RADIOTRACERS, PLACEBOS AND DEVICES

If this section (or one of its parts, A or B) is not applicable, state N/A and delete the rest of the section.

# A. DRUGS, BIOLOGICS and RADIOTRACERS

1. **Identification of Drug, Biologic or Radiotracer:** What is (are) the **name(s)** of the drug(s) biologic(s) or radiotracer(s) being used? Identify whether FDA approval has been granted and for what indication(s).

Topical tofacitinib ointment has been studied for the treatment of psoriasis and atopic dermatitis (phase II trials) but is not currently FDA-approved. The oral form of tofacitinib citrate is FDA-approved for the treatment of adults with moderately to severely active rheumatoid arthritis (RA) who have had an inadequate response to, or who are intolerant of, methotrexate.

All protocols which utilize a drug, biologic or radiotracer **not** approved by, but regulated by, the FDA, or a radiotracer regulated by the RDRC, must provide the following information:

a. What is the Investigational New Drug (IND) number assigned by the FDA? 203214

b. Who holds the IND? Pfizer

c. All protocols which utilize a radiotracer not approved by, but regulated by the FDA must provide the IND number:

Alternatively, use of the investigational radiotracer may be under RDRC/RSC oversight: (check if appropriate)\_\_\_\_\_

For all investigational radiotracers, attach a copy of the RDRC/RSC application (for radioisotopes used in the PET Center, PET Center personnel may complete this step) Go to http://rsc.med.yale.edu/login.asp?url=myApps.asp. When you have logged in, complete the application and attach a copy to this submission.

Alternatively, an **exemption from IND filing requirements** may be sought for a clinical investigation of a drug product that is lawfully marketed in the United States. If there is no IND and an exemption is being sought, review the following categories and complete the category that applies *(and delete the inapplicable categories)*:

## Exempt Category 1

The clinical investigation of a drug product that is lawfully marketed in the United States can be exempt from IND regulations if all of the following are yes:

- i. The intention of the investigation is NOT to report to the FDA as a well-controlled study in support of a new indication for use or to be used to support any other significant change in the labeling for the drug.  $\Box$  Yes  $\Box$  No
- ii. The drug that is undergoing investigation is lawfully marketed as a prescription drug product, and the intention of the investigation is NOT to support a significant change in the advertising for the product.  $\Box$  Yes  $\Box$  No
- iii. The investigation does NOT involve a route of administration or dosage level or use in populations or other factor that significantly increases the risks (or decreases the acceptability of the risks) associated with the use of the drug product. Yes No
- iv. The investigation will be conducted in compliance with the requirements for institutional (HIC) review and with the requirements for informed consent of the FDA regulations (21 CFR Part 50 and 21 CFR Part 56). Yes No
- v. The investigation will be conducted in compliance with the requirements regarding promotion and charging for investigational drugs. Yes No
- 2. **Background Information:** Provide a description of previous human use, known risks, and data addressing dosage(s), interval(s), route(s) of administration, and any other factors that might influence risks. If this is the first time this drug is being administered to humans, include relevant data on animal models.

Oral tofacitinib was approved by the FDA in 2012 for the treatment of moderate to severe rheumatoid arthritis (RA) who have had an inadequate response to, or who are intolerant of, methotrexate. It is likely to be approved by the FDA in the next 4-8 weeks for the treatment of psoriasis. Its use is currently being studied in a variety of other inflammatory diseases, including psoriatic arthritis, ankylosing spondylitis, juvenile idiopathic arthritis, Crohn's disease, and ulcerative colitis (clinicaltrials.gov).

Topical tofacitinib 2% ointment has been demonstrated to be well-tolerated and effective for the treatment of plaque psoriasis. It has also been studied in a phase II trial for atopic dermatitis (results not yet published).

The following table presents the risks as summarized in the package insert for **oral** XELJANZ. As mentioned above, the risks are likely to be far lower or nonexistent with topical administration because of minimal transepidermal absorption and the limited surface area of application being proposed in this study. As stated in Pfizer's investigator brochure, based on in vitro data, systemic bioavailability is predicted to be low ( $\leq$ 3%) following topical dosing relative to the oral route of administration.

**Table 1:** Adverse Effects with the use of oral tofacitinib citrate. The following data includes two phase 2 and five phase 3 doubleblind, controlled, multicenter trials. In these trials, patients were randomized to doses of XELJANZ 5 mg twice daily (292 patients) and 10 mg twice daily (306 patients) monotherapy, XELJANZ 5 mg twice daily (1044 patients) and 10 mg twice daily (1043 patients) in combination with DMARDs (including methotrexate) and placebo (809 patients). All seven protocols included provisions for patients taking placebo to receive treatment with XELJANZ at Month 3 or Month 6 either by patient response (based on uncontrolled disease activity) or by design, so that adverse events cannot always be unambiguously attributed to a given treatment. Comparisons between placebo and XELJANZ were based on the first 3 months of exposure, and comparisons between XELJANZ 5 mg twice daily and XELJANZ 10 mg twice daily were based on the first 12 months of exposure.

Adverse effect	Tofacitinib citrate:	Tofacitinib citrate:	Placebo	Notes:
	5 mg twice daily	10 mg twice daily		
Percentage of patients with any adverse effect requiring discontinuation of therapy.	4%	4%	3%	Any adverse reaction during the 0-3 months exposure in the double-blind, placebo-controlled trials.
Overall infection:	20%	22%	18%	Most common reported infections were URI, nasopharyngitis and UTI with a rate of 4%, 3% and 2%, respectively.
Serious infection: 0-3 months of therapy.	11 patients (1.7 events per 100 patient-years)	11 patients (1.7 events per 100 patient-years)	1 patient (0.5 events per 100 patient-years)	Most common serious infections included pneumonia, cellulitis, herpes zoster and UTI. The rate difference between treatment groups (and the corresponding 95% confidence interval) was 1.1 (-0.4, 2.5) events per 100 patient-years for the combined 5 mg twice daily and 10 mg twice daily tofacitinib group minus placebo.
Serious infection: 0-12 months of therapy.	34 patients (2.7 events per 100 patient-years)	33 patients (2.7 events per 100 patient-years)	N/A	Most common serious infections included pneumonia, cellulitis, herpes zoster and UTI. The rate difference between tofacitinib doses (and the corresponding 95% confidence interval) was -0.1 (-1.3, 1.2) events per 100 patient-years for 10 mg twice daily tofacitinib minus 5 mg twice daily tofacitinib.
Tuberculosis: 0-3 months of therapy	0	0	0	During the 0 to 3 months exposure, tuberculosis was not reported in patients who received placebo, 5 mg twice daily of tofacitinib, or 10 mg twice daily of tofacitinib.

Tuberculosis: 0-12 months of therapy	0	6 (0.5 events per 100 patient-years)	N/A	The rate difference between tofacitinib doses (and the corresponding 95% confidence interval) was 0.5 (0.1, 0.9) events per 100 patient-years for 10 mg twice daily tofacitinib minus 5 mg twice daily tofacitinib. Cases of disseminated tuberculosis were also reported. The median tofacitinib exposure prior to diagnosis of tuberculosis was 10 months (range from 152 to 960 days).
Opportunistic infections (excluding tuberculosis): 0-3 months of therapy	0	0	0	In the seven controlled trials, during the 0 to 3 months exposure, opportunistic infections were not reported in patients who received placebo, 5 mg twice daily of tofacitinib, or 10 mg twice daily of tofacitinib.
Opportunistic infections (excluding tuberculosis): 0-12 months of therapy	4 (0.3 events per 100 patient-years)	4 (0.3 events per 100 patient-years)	N/A	The rate difference between tofacitinib doses (and the corresponding 95% confidence interval) was 0 (-0.5, 0.5) events per 100 patient-years for 10 mg twice daily tofacitinib minus 5 mg twice daily tofacitinib.
Malignancy: 0-3 months of therapy.	2 patients (0.3 events per 100 patient-years)	2 patients (0.3 events per 100 patient-years)	0	Most common types of malignancy were lung and breast cancer, followed by gastric, colorectal, renal cell, prostate cancer, lymphoma and malignant melanoma. The rate difference between treatment groups (and the corresponding 95% confidence interval) was 0.3 (-0.1, 0.7) events per 100 patient-years for the combined 5 mg and 10 mg twice daily tofacitinib group minus placebo.
Malignancy: 0-12 months of therapy	5 patients (0.4 events per 100 patient-years)	7 patients (0.6 events per 100 patient-years)	N/A	One of these malignancies was a case of lymphoma that occurred during the 0 to 12 month period in a patient treated with tofacitinib 10 mg twice daily. The rate difference between tofacitinib doses (and the corresponding 95% confidence interval) was 0.2 (-0.4, 0.7) events per 100 patient-years for 10 mg twice daily tofacitinib minus 5 mg twice daily tofacitinib.

Lymphopenia: confirmed decreases in absolute lymphocyte counts below 500 cells/mm  .	0.04%	0.04%	N/A	Confirmed lymphocyte counts less than 500 cells/mm3 were associated with an increased incidence of treated and serious infections.
Neutropenia: ANC below 1,000 cells/mm  .	0.07%	0.07%	N/A	There were no ANC below 500 cells/mm  observed in any treatment group. There was no clear relationship between neutropenia and the occurrence of serious infections.
Liver enzyme elevations: percentage of patients with ALT elevations >3x ULN on DMARD trials.	1.3%	1.2%	1.0%	No elevations of liver enzymes were seen in controlled monotherapy with tofacitinib.
Liver enzyme elevations: percentage of patients with AST elevations >3x ULN on DMARD trials.	0.5%	0.4%	0.6%	No elevations of liver enzymes were seen in controlled monotherapy with tofacitinib.
Lipid elevations: Mean LDL cholesterol	Increased by 15%	Increased by 19%	N/A	Dose-related elevations in lipid parameters (total cholesterol, LDL cholesterol, HDL cholesterol, triglycerides) were observed at one month of exposure and remained stable thereafter.
Lipid elevations: Mean HDL cholesterol	Increased by 10%	Increased by 12%	N/A	Dose-related elevations in lipid parameters (total cholesterol, LDL cholesterol, HDL cholesterol, triglycerides) were observed at one month of exposure and remained stable thereafter.
Lipid elevations: Mean LDL/HDL ratios	Unchanged	Unchanged	N/A	
Serum creatinine elevations:	Mean increase in serum creatinine was < 0.1 mg/dL	Mean increase in serum creatinine was < 0.1 mg/dL		Dose-related elevations in serum creatinine were observed with tofacitinib treatment.
				Up to 2% of patients were discontinued from tofacitinib treatment due to the protocol-specified discontinuation criterion of an increase in creatinine by more than 50% of baseline. The clinical significance of the observed serum creatinine elevations is unknown.

ANC: absolute neutrophil count, DMARD: disease-modifying anti-rheumatic drug, ULN: upper limit of normal, URI: upper respiratory infection, UTI: urinary tract infection

## Page 17 of 26

- 3. Source: a) Identify the source of the drug or biologic to be used.
  - Pfizer Pharmaceuticals
  - b) Is the drug provided free of charge to subjects?  $\boxtimes$  Yes  $\square$  No
    - If yes, by whom? Pfizer
- 4. **Storage, Preparation and Use:** Describe the method of storage, preparation, stability information, and for parenteral products, method of sterilization and method of testing sterility and pyrogenicity.

Check applicable Investigational Drug Service utilized:

- YNHH IDS
  - **CMHC Pharmacy**

Yale Cancer Center West Haven VA None N/A

**PET Center** Other:

Note: If the YNHH IDS (or comparable service at CMHC or WHVA) will not be utilized, explain in detail how the PI will oversee these aspects of drug accountability, storage, and preparation.

